6.13. Clinical Laboratory Tests

Subjects will be required to fast overnight prior to collection of Clinical Laboratory Samples.

All subjects undergo screening via a blood test to rule out human immunodeficiency virus (HIV), Hepatitis B and C.

Serum human chorionic gonadotrophin will be determined in WOCBP at screening. A urine pregnancy test will be conducted in WOCBP upon admission (Day -3).

Urine will be collected for drug screening as well as urinalysis. Urinalysis will be assessed by dipstick analysis. Microscopic examination will be undertaken if there is an abnormality warranting further investigation.

An alcohol breath test will be conducted at Screening to determine eligibility.

Blood samples will be collected for hematology and serum chemistry as well as coagulation parameters.

Subjects will be in a seated or supine position during blood collection. A list of the clinical laboratory tests is provided in [Appendix 5](#). Please refer to the SOA in [Appendix 1](#) and [Appendix 2](#) for details regarding timing for assessments.

6.14. Sample Collection, Storage, and Shipping

The site shall obtain, process, and freeze blood samples (at temperatures as per study manual) for the listed tests in preparation for shipment to a bioanalytical laboratory for analysis. Full details pertaining to the collection, handling, and shipment of these samples are provided in the laboratory manual. Safety laboratory assessments will be performed locally at the study site's laboratory, based on its established methods.

6.14.1. Handling, Storage, and Destruction of Biological Samples

After analysis, samples will be disposed of or retained for further use as described below. Any PK sample remaining after analysis for KNX100 and its metabolites, may be used for exploratory biomarker analyses. These analyses are for Sponsor use only and will not be included in the clinical study report.

Any biological samples collected for future research will be retained by the Sponsor or designee for a maximum of 15 years following the finalization of the clinical study report. The results from future analysis will not be reported in the clinical study report.

6.14.2. PK Samples

Incurred sample reproducibility analysis, if any, will be performed alongside the bioanalysis of the test samples and reported in a separate bioanalytical report. Samples for metabolite identification and/or analysis will be performed as an exploratory endpoint in this study. The results from the investigation(s) may not be reported in the clinical study report but will be reported separately in a PK report.

6.14.2.1. Timing of PK samples

Refer to [Appendix 3](#) for details on the timing of PK samples. If more than one assessment is foreseen for a timepoint, assessments should be staggered in the same order throughout the study with the PK sampling point closest to the scheduled timepoint.

6.14.3. Collection of Plasma for Exploratory Analysis of PD Biomarkers

All subjects may also be asked to provide plasma samples which may be used to further investigate the relationship between PK and blood-borne biomarkers (yet to be identified).

Please refer to the SOA in [Appendix 1](#) and [Appendix 2](#) for details regarding timing for assessments.

6.15. End of Study Visit/Early Termination Visit

The End of Study (EOS)/Early Termination (ET) Visit will occur 7 days after last dose (± 2 days) for Part 1 (SAD) and 7 days after the last dose (± 2 days) for the MAD part of the study. This visit can also take place if a subject withdraws early from the study.

A serum pregnancy test will be performed for WOCBP. Hematology and coagulation, biochemistry, and urinalysis will be performed. The subject will be asked about AEs and prior and concomitant medications and an ECG will be conducted. Every attempt will be made for collection of data from withdrawn subjects via attendance to an EOS/ET Visit.

6.16. Dispensing Study Drug

The site pharmacy (or equivalent) associated with the study site is responsible for dispensing the appropriate randomized/blinded study product to site staff for dosing onsite. Dose escalation will progress upon CRC approval (refer to [Section 9.8](#)).

6.17. Adverse Events Assessments

Any new event or experience that was not present at Screening, or the worsening of an event present at Screening, is considered an AE ([Section 6.17.1](#)). The investigator is responsible for following all AEs from onset to adequate resolution (event is resolved or subject is medically stable), where possible ([Section 6.17.8](#)).

AEs will be documented from physical or neurological examination findings, clinically significant laboratory results (as per reference ranges indicated in the Study Procedures and Laboratory Manuals), vital signs, ECGs, EEGs, or any other assessments that are relevant to subject safety.

The PI is responsible for reporting of all safety events that occur within the AE reporting period and will classify severity ([Section 6.17.3](#)) and relationship to study drug ([Section 6.17.4](#)) for each event. Any event that meets the definition of a serious adverse event (SAE; [Section 6.17.10](#)) will be recorded and reported as an SAE.

The PI or designee is responsible for recording all AEs on the appropriate study specific CRF, regardless of the AE's likely relationship to study treatment. Any changes in severity of an AE will be recorded and any AEs characterized as intermittent will be documented for each episode.

The CRF has been designed to capture the data elements recommended for reporting of drug safety events under current International Conference on Harmonisation (ICH) guidelines (ICH E2A, E6).

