Subjects will be housed in the clinic from Day -3 prior to study drug administration and will remain in-house for 30 hours postdose (Day 2) for PK and safety assessments.

[figure not shown]
Part B (MAD) will evaluate up to 3 doses based on doses established during Part A (SAD). Each subject will receive 7 doses of study drug, administered either once (Cohorts 1 and 2) or twice daily (Cohort 3). All subjects in each MAD cohort will have their AE, PK, and electroencephalography (EEG) data, acquired up to and including Day 8, evaluated for safety and tolerability by the CRC before opening the next higher dose cohort. Subjects will be housed in the clinic from Day -3 prior to study drug administration and will remain in-house for 24 hours post morning dose (Day 8) for PK and safety assessments.

The study will be comprised of 3 periods: Screening (up to 28 days); Treatment (1 day for the SAD subjects and 7 days for MAD subjects) and Follow-up. Subjects will have a follow-up visit 7 days after the last dose. As SAD dosing is a single dose on Day 1, follow-up will occur

on Day 7. MAD dosing involves either single daily dosing (Cohorts 1 and 2) or twice daily dosing (Cohort 3) on Days 1 to 7, with a follow-up visit occurring on Day 14.

The overall study design is summarized in Figure 1. Refer to Appendix 1 and Appendix 2 for a detailed schedule of assessments.

Figure 1 Study Phases and Activities

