6.4. Physical and Neurological Examinations

A medical assessment will be completed by the principal investigator (PI) or a study physician at study entry, and at any early withdrawal visits. The primary purpose of the medical assessment at study entry is to confirm the subject's suitability to enroll in the study.

The physical examination will include height (screening only), body weight, and an evaluation of the head, eyes, ears, nose, and throat, and the cardiovascular, dermatological, musculoskeletal, respiratory, gastrointestinal, and neurological systems. Record any abnormality identified prior to administration of study medication as medical history.

Any clinically significant, new, or worsened abnormalities that occur after administration of study medication should be recorded as AEs. Additional parameters may be assessed as indicated by any subject symptoms.

Abbreviated physical examinations performed throughout the study should be symptom-directed.

Neurological examination shall include assessment of cranial nerves, motor, sensation, coordination, reflexes, and gait. Abbreviated neurological examinations performed throughout the study include light touch/power in limbs and brief cranial nerve examination.

Findings will be recorded as normal/abnormal for each parameter with additional description as indicated. All abnormal, clinically significant, findings will be considered AEs.

Please refer to the Schedule of Assessments (SOA) in [Appendix 1](#) and [Appendix 2](#) for details regarding timing for assessments.

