6.17.1. Definition

This study will follow the definition of “adverse events” as specified in ICH E2A:

“Any untoward medical occurrence in a subject or clinical investigation subject administered a pharmaceutical product and which does not necessarily have to have a causal relationship with this treatment.”

An AE can therefore be any unfavorable and unintended sign (including an abnormal laboratory finding, for example), symptom, or disease temporally associated with the use of a medicinal product, whether or not considered related to the medicinal product.

An AE **does not** include:

- Pre-existing diseases or conditions present or detected at screening/baseline that do not worsen in severity or frequency.
- Hospitalization for evaluation or treatment of a condition that predated the initial dose of blinded study product and has not worsened in severity since that initial dose.
- Situations where an untoward medical occurrence has not occurred.
 - e.g., hospitalization for elective surgery, social and/or convenience admissions.
- Medical or surgical procedures (e.g., surgery, endoscopy, tooth extraction, transfusion)
 - Of note however, the condition that leads to the procedure **is** an AE, unless the condition pre-dated the initial dose of blinded study product and has not worsened in severity since that initial dose.
- Overdose of either study drug or concomitant medication without any signs or symptoms.

All AEs are classified as serious or non-serious. Refer to [Section 6.17.10](#) for definition of an SAE.

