6.4.1 Adverse Events

An adverse event (AE) is recorded if it is a new event that was not present at Screening, or is the worsening of an event present at Screening. A treatment-emergent adverse event (TEAE) is defined as any AE that starts or worsens after first dose of study drug. Partial start dates will be imputed according to Appendix 1 for the determination of treatment-emergence. Any AEs with missing start time that occur or worsen on study day 1 will be assumed to be treatment-emergent.

AEs will also be assessed for outcome, severity, relationship to study drug, and seriousness. Any missing severity assessments will be assumed to be Grade 3 (severe) and missing relationship assessments will be assumed to be related. Expected AEs related to KNX100 treatment are provided in the KNX100 Investigator's Brochure. Adverse events will be coded based on the MedDRA for reporting by SOC and PT. SOC's will be ordered in accordance with the international agreed upon sort order for SOC followed by descending order of overall incidence. The MedDRA version used for reporting will be described in the relevant table and listing footnotes.

An overview of TEAEs will be produced, including counts and percentages of subjects as well as number of events by study part and cohort with any incidences of: TEAEs, TEAEs grade 3 or higher, TESAEs, TEAEs related to study treatment, and TESAEs related to study treatment.

Summaries of adverse events by SOC and PT will present the number and percentage of total subjects and number of events (where noted below) by study part and cohort and will include the following types:

- TEAEs (including number of events)

- TEAEs by maximum severity
- TEAEs by highest relationship to study treatment
- Treatment-emergent SAEs

When calculating the incidence of AEs, each AE will be counted only once for a given subject within a MedDRA category (e.g., overall, system organ class, or preferred term), but all occurrences of the same event will be counted in the number of events. When AEs are summarized within levels of another AE assessment (e.g., relatedness or severity), AEs will be counted once per subject at the worst/highest level of the assessment (e.g., highest relationship to study drug or greatest severity).

A comprehensive listing of all adverse events will be provided in a by-subject data listing. In addition, a listing of all treatment-emergent SAEs will be provided.

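### The reference state for an adverse event differs between Protocol 6.17, 6.17.1, 6.4 and the SAP, so a symptom that clears before dosing and returns at the same grade can go unrecorded

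*Protocol*

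**What the plan says.** Several places govern what is recorded as an AE, and they do not share a reference time.

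- **Protocol 6.17:** "Any new event or experience that was not present at Screening, or the worsening of an event present at Screening, is considered an AE". The sentence then refers to 6.17.1. The same section asks for each episode of an intermittent AE to be documented.
- **SAP 6.4.1:** "An adverse event (AE) is recorded if it is a new event that was not present at Screening", or a worsening of one that was.
- **Protocol 6.17.1** adopts the ICH E2A definition, which begins "Any untoward medical occurrence in a subject or clinical investigation subject administered a pharmaceutical product" and makes no comparison with Screening. Its list of what is not an AE includes "Pre-existing diseases or conditions present or detected at screening/baseline that do not worsen in severity or frequency". It also includes "Hospitalization for evaluation or treatment of a condition that predated the initial dose of blinded study product", provided there has been no worsening since that dose. The bullet on procedures uses the same reference.
- **Protocol 6.4:** "Any clinically significant, new, or worsened abnormalities that occur after administration of study medication should be recorded as AEs". For the pre-dose period: "Record any abnormality identified prior to administration of study medication as medical history".
- **Protocol 6.2** collects AEs from the signing of consent. Appendices 1 and 2 mark AEs at Screening and on Day -1.
- **TEAE definitions:** Protocol 6.17.2 takes AEs with onset between first dose and 24 hours after the last dose. SAP 6.4.1 takes AEs with onset or worsening after first dose.
- **SAP 5.2:** for endpoints other than ECG and EEG, baseline is the last non-missing value before first dose.

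**The concern.** TEAE incidence heads the list of primary safety endpoints (Protocol 8.5.1, SAP 2), and the Cohort Review Committee looks at AEs before each escalation (Protocol 5.3.4 and 9.8.1). A rule about what goes on the AE form acts before any analysis: an event that the site does not enter is out of reach of the TEAE programming, however carefully that is specified.

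A Screening reference answers the wrong question for treatment emergence. What matters is whether the subject's state changed from just before dosing. A subject who had a headache at the screening visit, was well on Day 1 before dosing and has a headache again after dosing has changed, yet the Screening comparison shows no change. With six active subjects per cohort, a single omission is visible in the percentages.

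**Working it through.** No sample-size or power figure bears on this point, so the check is a timing calculation and a side-by-side reading.

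**1. Timing.** Appendices 1 and 2 place Screening at Day -28 to Day -2. Under the Study Day rule in SAP 5.2, a date before treatment start is numbered as date minus start date, so there is no Day 0. Day -28 is 28 days before dosing and Day -2 is 2 days before. The Screening reference is therefore 2 to 28 days old at first dose; 28 is a maximum.

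**2. Three test cases** (grades are illustrative).

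- A: Grade 1 at Screening, absent just before dosing, Grade 1 after dosing.
- B: Grade 2 at Screening, Grade 1 just before dosing, Grade 2 after dosing.
- C: absent at Screening, first found on Day -1, unchanged after dosing.

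| Rule | A | B | C |
|---|---|---|---|
| Protocol 6.17 and SAP 6.4.1, literal | Neither new nor worse; can be omitted | Not worse than Screening; can be omitted | AE |
| Protocol 6.17.1 exclusion, if Screening governs | Excluded, unless the return counts as higher frequency | Excluded, unless frequency rose | Not excluded |
| Protocol 6.17.1 exclusion, if pre-dose baseline governs | Not excluded; AE | Worse; AE | Excluded |
| Protocol 6.4 (examination findings) | AE if clinically significant and taken as new | AE if clinically significant and taken as worsened | Medical history |
| Protocol 6.2 | Not addressed | Not addressed | Collected as an AE |

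The slash in the 6.17.1 exclusion leaves open which of its two rows applies, and the answer changes with the choice in all three cases. In case C, 6.4 also conflicts within itself: its closing paragraph treats every clinically significant abnormal finding as an AE, with no time limit.

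**3. Can the TEAE rules repair A and B?** No. Both start from the set of AEs. If A is recorded with onset after first dose, it is a TEAE under the SAP, and under the Protocol if onset is within 24 hours of the last dose. If it is not recorded, neither rule sees it. Case C is not a TEAE under either document, so it affects the consistency of the AE and medical-history data but not TEAE incidence.

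**4. What would other data still show?**

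- Part B bowel changes are recorded daily (Protocol 6.6), and SAP 6.4.7 tabulates gastrointestinal symptoms by visit, whether or not they are AEs.
- Laboratory values, vital signs and ECG are summarised as change from a pre-dose baseline (SAP 5.2, 6.4.2, 6.4.3, 6.4.5).
- EEG activity is tabulated by visit (SAP 6.4.6), and Protocol 6.17.6 makes interictal discharges emerging after dosing a suspected adverse reaction.

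This leaves mainly symptoms that the subject reports and that have no scheduled assessment. In Part A these include gastrointestinal symptoms, because SAP 6.4.7 has no such assessment there.

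**5. Size.** Each cohort has 6 subjects on KNX100. One missed subject changes the incidence of that event by 1/6 = 16.7 percentage points. The incidence of any TEAE changes by that amount only if the subject has no other TEAE. A count of missed events would need the share of subjects with a symptom that clears before dosing, the chance that it returns at no more than its Screening grade, and the chance that the investigator applies the literal rule. The documents give none of these.

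**The case against.** The strongest reply is that 6.17 sends the reader to 6.17.1, where the governing definition is ICH E2A. That covers any untoward occurrence, and the relevant exclusion names baseline as well as screening and lets higher frequency count as worsening. Neither Screening sentence says that only such events are AEs. On that reading, case B is worse than baseline, and case A is either a new occurrence or a rise in frequency. Section 6.4 adds clinically significant findings on examination, and the rule on intermittent AEs adds further episodes.

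Much of this stands. A reader might infer that a returning symptom is not an AE and cannot be a TEAE. The documents do not support so absolute a statement, because 6.17.1 allows it to be recorded and then counted. But 6.17.1 does not clearly require it: a condition detected at Screening that returns at the same grade can equally fall under the exclusion. The intermittent rule applies only to something already classed as an AE. Section 6.4 covers examination findings and does not say what new is measured against. The SAP carries none of these qualifiers.

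Four other stronger readings also fail:

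- That no analysis could show the recurrences: step 4 above lists those that would be seen.
- That the Day -2 sleep-deprived EEG falls between Screening and dosing: the schedules and SAP 5.2 place it within Screening.
- That the hospitalisation bullet removes the underlying condition: it excludes only the admission.
- That the loss can be counted: if 5% to 20% of subjects (assumed) had a finding that cleared before dosing, 42 × 0.05 = 2.1 to 42 × 0.20 = 8.4 of the 42 planned active subjects (7 cohorts × 6) would be exposed to the gap. These are not missed events, and screening for health may make the true share small.

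**Conclusion.** The inconsistency is real and worth correcting. The documents use Screening, screening/baseline, the initial dose and administration of study medication as reference times for the same decision, and the SAP repeats only the Screening version. A symptom that cleared before dosing and returns at the same grade can be left off the AE form, and nothing downstream restores it as a TEAE. An abnormality first found on Day -1 is given opposite instructions.

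The conclusion rests on a literal reading of 6.17 and SAP 6.4.1; an investigator who works from 6.17.1 may well record the event. The rule applies to KNX100 and placebo alike, so the supported statement is possible under-capture. A reader might infer bias between arms, but nothing in the documents shows it. The number of events is unknown; the scale is the 16.7 points per missed subject within an active cohort.

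**What to change.** - In Protocol 6.17 and SAP 6.4.1, replace the Screening reference. Judge treatment emergence against the subject's state immediately before first dose, and state that recurrence after resolution, or worsening from the pre-dose state, counts as a new AE.
- Reconcile Protocol 6.4 and 6.17.1 with 6.2, so that events arising between consent and first dose are recorded as AEs that are not treatment-emergent and do not go to medical history.
- Protocol 3.2.1 cites human data already obtained, so dosing has begun. The clarification should therefore reach the site as well as the SAP, and do so before database lock.

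The cost is wording in four sections, with no new procedures or assessments. The downside is a few more mild AEs recorded in both arms.

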6.17.1. Definition

This study will follow the definition of “adverse events” as specified in ICH E2A:

“Any untoward medical occurrence in a subject or clinical investigation subject administered a pharmaceutical product and which does not necessarily have to have a causal relationship with this treatment.”

An AE can therefore be any unfavorable and unintended sign (including an abnormal laboratory finding, for example), symptom, or disease temporally associated with the use of a medicinal product, whether or not considered related to the medicinal product.

An AE **does not** include:

- Pre-existing diseases or conditions present or detected at screening/baseline that do not worsen in severity or frequency.
- Hospitalization for evaluation or treatment of a condition that predated the initial dose of blinded study product and has not worsened in severity since that initial dose.
- Situations where an untoward medical occurrence has not occurred.
 - e.g., hospitalization for elective surgery, social and/or convenience admissions.
- Medical or surgical procedures (e.g., surgery, endoscopy, tooth extraction, transfusion)
 - Of note however, the condition that leads to the procedure **is** an AE, unless the condition pre-dated the initial dose of blinded study product and has not worsened in severity since that initial dose.
- Overdose of either study drug or concomitant medication without any signs or symptoms.

All AEs are classified as serious or non-serious. Refer to [Section 6.17.10](#) for definition of an SAE.

6.17.2. Timing and Reporting Period

Treatment-emergent adverse events (TEAEs) are defined as any AE starting during the active treatment period (from first dose to 24 hours after the last dose of study treatment).

If an AE causes a subject to discontinue the study, the PI remains responsible for following the AE until the event is resolved or explained. Frequency of follow-up evaluation is left to the discretion of the PI.

In addition, any known untoward event that occurs subsequent to the AE-reporting period that the PI assesses as related to the study drug should also be reported as an AE.

